Already, there are several reports of increased immunogenicity with additional dosing of vaccination¹². Randomized controlled trial comparing placebo vs. other mRNA vaccine as a booster dose study showed some benefit¹³. However, as of now, there is no comparison study between mRNA and adenovirus vector vaccine. This time, we are conducting single center randomized controlled trial comparing mRNA vs. Adenovirus vector vaccine as a third dose after completion of two doses of mRNA vaccine in solid organ transplant recipients.

3) Inclusion and Exclusion Criteria*

Inclusion Criteria:

- *Patients 18 years of age and older*
- *Patients who had received a solid organ (kidney, liver, lung, heart, and pancreas) transplant patient from living or deceased donors.*
- *Patients with active graft with at least one immunosuppressive medication*
- *Completed two doses of BNT162b2 vaccination at least 28 days ago*

Exclusion Criteria:

- *Patient with non-active graft*
- *Any significant side effect with previous COVID-19 vaccination*
- *Within 28 days of BNT162b2 vaccine completion*
- *Already received more than and equal to three doses of COVID-19 vaccination*
- *Previously received COVID-19 vaccine other than BNT162b2 vaccine*
- *Previously received monoclonal Antibody treatment that are specifically directed against the spike protein for SARS-CoV-2 such as Mab, Bamlanivimab, etesevimab, Casirivimab, imdevimab, Sotrovimab and/or any combination.*

IRB Study Number: 20210641
 Version #4, Date: October 26, 2021

- *Thrombocytopenia (listed as a medical diagnosis or less than 50,000 per microliter 30 days prior vaccination)*
- *History of Capillary Leak Syndrome*
- *Adults unable to consent*
- *Individuals who are not yet adults (younger than 18 year old)*
- *Vulnerable patients (prisoners)*
- *Pregnant women*

4) Evaluation

Evaluation will be conducted as below schedule.

Procedures	Screening	Enrollment/Baseline Visit 1, Day 1	Phone Call Visit 2 48-96 hours	Phone Call Visit 3 6-8 days	Study Visit 4 Day 28 +/- 7 day	Study Visit 5 Month 6 (+/- 7 days)	Study Visit for Sub study only At Month 6 (+/- 30 days)
Informed consent	X	X					
Demographics	X	X					
Medical history	X	X					
Randomization	X	X					
Blood sample collection		X			X		X*
Vaccine Administration		X					
Symptom checker		X	X	X	X		
Phone call follow up			X	X	X	X	

* 50 optional participants only

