Blood samples will be obtained from all patients at the time of enrollment (Day 1) and day 28 to test IgG and IgM against SARS-CoV-2 spike protein.

IRB Study Number: 20210641
Version #4, Date: October 26, 2021

At month 6, 50 optional patients will join to participate in the sub-study which will consist of blood sample collection to measure long term immunogenicity (IgG and IgM).

5) Sample Size calculation

The primary outcome of this study is IgG positivity after 28 (21-35) days of the booster dose of the either vaccine. This IgG should be antibody against spike protein, and reported as RBD, measured by [name] lab. We put alfa of 0.05 and beta of 0.2. The IgG positivity in JNJ-78436735 should be assumed as 80% and BNT162b2 as 60%.

6) Number of Subjects*

The Number needed in this study should be 93 per one arm, which is 186 in total. We assume 5-10% follow-up lost so we are going to enroll 200 patients in total.

For sub study to measure long term immunogenicity, we will enroll 50 patients among 200 participants.

The participants will be contacted via phone call in 6 months for monitoring.

7) Description of the study

This is the patient-blinded randomized controlled trial. To monitor patient reporting side effect properly, we are going to conduct the patient-blinded. Study team member will be aware after randomization, at the time of giving vaccination. This is not observer blinded. Also, to minimize bias, [name] lab members will not be notified which vaccine each participant receives. Randomization will be conducted via excel by [name]. Adult transplant recipients will be recruited from outpatient clinics. Transplant patients will be randomized in a 1:1 ratio.

8) Randomization of vaccine

A randomization schedule will be created using Microsoft Excel. [name] will randomly select 100 numbers out of 200 using excel. The selected number patients will receive JNJ-78436735 vaccine. The rest will receive BNT162b2 vaccine. Those randomized result will put into 200 envelopes. On top of each envelope, only study ID, from 001 to 200, will be written. The envelope will be filed in each patient's research chart. Charts will be located at the research office located at the Elliot Building. Only the study team will have access to the building.

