The sample size was based on previous studies, which had indicated a response rate of approximately 50% and 70% to each vaccine.

Therefore, for an alpha of 0.05 and a power of 80%, a sample size of 93 evaluable patients in each study group should be required. As we assume 10% of the patients will not be back, we have that margin and going to enroll 200 patients in total. The immunogenicity analysis will be only performed in those who received a vaccine dose and returned for follow-up serum (per-protocol population). The safety analysis will be performed in all patients who received the study vaccine regardless of whether they returned for follow-up serum. Demographics will be analyzed using descriptive statistics. Differences in vaccine response rates between the 2 arms will be compared using χ^2 test. Pre- and post-vaccination titers will be compared using Wilcoxon rank-sum test. Univariate analyses will be performed to determine significant factors affecting seroconversion using χ^2 test for categorical variables and Mann-Whitney U test for continuous variables. We will develop multivariate model to determine the factor of positive IgG post booster dosing. For multivariate analysis, a model should be developed using variables that had a P value < 0.2 on univariate analysis. Multivariate analysis will be performed using

IRB Study Number: 20210641
Version #4, Date: October 26, 2021

binary logistic regression. Statistical significance was defined as a P value < 0.05. Statistical analysis will be performed using IBM SPSS version 26.0.

15) Provisions to Monitor the Data to Ensure the Safety of Subjects*

Study Auditing and Monitoring

This study will be monitored (as applicable) and may be audited according to the University of Miami requirements. See also

<http://research.med.miami.edu/clinical-research/crors/monitoring>

Clinical Research Operations & Regulatory Support CRORS will provide internal study monitoring compliance. Following the monitoring plan, the monitors will verify that the clinical trial is conducted and data are generated and biological specimens are collected, documented (recorded), and reported in compliance with the protocol, International Conference on Harmonization Good Clinical Practice (ICH GCP), and applicable regulatory requirements.

Trial Monitoring, Auditing, and Inspecting

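### The risk-factor model screens on an undefined outcome, selects by univariate P < 0.2 in the same data, and does not guarantee that randomised arm or Day 1 IgG stays in

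*Combined protocol and SAP*

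**What the plan says.** The statistical paragraph in section 14 (Data Management) sets out a two-step search for factors related to response.

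- **Step 1, screen:** "Univariate analyses will be performed to determine significant factors affecting seroconversion", with a chi-square test for categorical and a Mann-Whitney test for continuous variables.
- **Step 2, model:** "We will develop multivariate model to determine the factor of positive IgG post booster dosing". This is a binary logistic regression, and "a model should be developed using variables that had a P value < 0.2 on univariate analysis".
- **Threshold:** "Statistical significance was defined as a P value < 0.05".

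Seroconversion is not defined and appears nowhere else. Candidate variables are not listed. The paragraph does not say whether randomised arm or Day 1 IgG is kept whatever its P value, and it describes no shrinkage, validation or multiplicity handling for the model.

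The primary endpoint is stated separately in section 5: "The primary outcome of this study is IgG positivity after 28 (21-35) days of the booster dose of the either vaccine". It has its own test: "Differences in vaccine response rates between the 2 arms will be compared using" a chi-square test.

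On baseline status, section 4 states: "Blood samples will be obtained from all patients at the time of enrollment (Day 1) and day 28 to test IgG and IgM". The inclusion criteria in section 3 require "Completed two doses of BNT162b2 vaccination at least 28 days ago", and the exclusion list does not mention IgG positivity at baseline.

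**The concern.** Three features of the procedure could distort the list of factors that the trial reports.

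1. **The outcome may change between steps.** In its ordinary sense seroconversion is a change from negative to positive, so a patient positive on Day 1 cannot convert but can be positive on Day 28. After two prior doses such patients may well be enrolled. The screen would then choose variables for one outcome and the model would test them on another.
2. **Selection is ignored in the final inference.** The variables reaching the model are those that already looked associated in the same data. Their P values and estimates are then read as though no selection had taken place.
3. **Arm and Day 1 IgG are not protected.** In a randomised comparison of two boosters, a model of who responds should contain the booster and the prior antibody level. As written, either can be left out by the screen.

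At stake is a published set of predictors of response in transplant recipients. The comparison of the two vaccines is not at stake.

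**Working it through.** **Inputs from the documents.** There are 93 evaluable patients per arm, 186 in all. Assumed positivity is 80% and 60% in section 5, and 50% and 70% in section 14. The screen is at 0.2 and the test at 0.05.

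**The plan's own figure.** The 93 per arm reproduces from 50% vs 70%, two-sided 0.05, 80% power: [1.960·√(2·0.6·0.4) + 0.842·√(0.25 + 0.21)]² / 0.20² = 93.0. The 60% vs 80% pair gives 82 without and 91 with a continuity correction. The plan states no sample size or event count for the risk-factor model.

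**Assumptions.** The documents give no number of candidates, effect sizes or Day 1 positivity. The simulations below use assumed ranges for these, with 186 patients and 1,000 to 1,500 runs per setting.

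**Check 1: null candidates, 60% positive.** About 20% of null variables pass the screen, as expected.

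| Candidates | Significant, given passed screen | False positives per original candidate | Any false factor, screened | Any false factor, full model without screen |
|---|---|---|---|---|
| 10 | 25% | 4.9% | 38% | 41% |
| 15 | 26% | 5.3% | 54% | 59% |
| 20 | 25% | 5.1% | 63% | 69% |

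The second column is close to 0.05/0.20 = 25%. A P value below 0.05 for a retained variable therefore carries much less weight than its face value. The last two columns show that the chance of at least one false factor is not raised by the screen. It is close to ordinary multiplicity: 1 − 0.95^k gives 40%, 54% and 64% for k = 10, 15 and 20.

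**Check 2: one true factor among 10 candidates.**

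| True odds ratio per SD | Kept by screen | Mean log odds ratio when kept ÷ truth | Same ratio, full model |
|---|---|---|---|
| 1.3 | 66% | 1.35 | 1.08 |
| 1.5 | 90% | 1.11 | 1.08 |
| 2.0 | 99.9% | 1.05 | 1.10 |

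The harm is concentrated on weak factors.

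**Check 3: which outcome is screened.** Assume a factor with odds ratio 2 per SD for Day 1 positivity and 1.5 per SD for conversion among Day 1 negatives. Day 1 positivity (at the factor's mean) is varied from 10% to 50%. Probability that the factor passes the screen:

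| Day 1 positive | Screen on Day 28 positivity | Screen on conversion, Day 1 negatives only | Screen on conversion, Day 1 positives counted as non-converters |
|---|---|---|---|
| 10% | 98% | 88% | 53% |
| 20% | 99% | 84% | 26% |
| 30% | 99.5% | 80% | 18% |
| 40% | 99.5% | 72% | 28% |
| 50% | 99.7% | 69% | 38% |

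In the last column at 30%, a real factor passes no more often than a null one would (20%). With no Day 1 positives the three outcomes coincide.

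**Check 4: randomised arm at the screen.** Arm fails if the observed difference lies within ±1.2816·SE₀. Here SE₀ = √(2p̄(1−p̄)/93), with p̄ the mean of the two rates, and the observed difference has standard error SE₁ = √([p₁(1−p₁) + p₂(1−p₂)]/93).

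- 60% vs 70%: the limit is 1.2816 × 0.0699 = 0.0896 and SE₁ = 0.0696. Φ((0.0896 − 0.10)/0.0696) = Φ(−0.149) = 0.441; subtracting the opposite tail (0.003) leaves **about 44%**. A separate simulation of 600 trials gave 45%.
- 60% vs 80%: the limit is 0.0861 and SE₁ = 0.0656. Φ(−1.736) = **about 4%**; simulation also gave 4%.
- 50% vs 70%: the limit is 0.0921 and SE₁ = 0.0703. Φ(−1.535) = **about 6%**.

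**Check 5: what the data can support.** Expected non-responders are 93·0.5 + 93·0.3 = 74.4 under 50/70, and 93·0.4 + 93·0.2 = 55.8 under 60/80. At an assumed 10 events per parameter this allows about 7 or 5 parameters in total.

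**The case against.** The best defence has four parts.

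**Seroconversion may be loose wording for IgG positivity.** This stands as far as it goes. The documents name one serological endpoint, and the paragraph moves between several terms for response. A reader might infer that two different outcomes are definitely being used, but the documents do not establish that. It would need both a negative-to-positive definition and participants positive on Day 1, and neither is given. What remains is an undefined term whose meaning can change which variables enter the model.

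**The screen does not create more false factors overall.** This also stands. A reader might take the 38-63% chance of at least one false factor, or the 25% conditional rate, to mean that the P < 0.2 rule multiplies false findings. It does not: per original candidate the rate is nominal, and the unscreened model does slightly worse. The valid point is narrower. The reported P values for retained variables ignore how those variables were chosen, and weak effects are overstated.

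**Real, strong factors are plausible and survive.** The background section expects immunosuppression to reduce response, and at odds ratios of 1.5 to 2 per SD the screen does little harm. It is therefore too strong to say that the reported factors will be unreliable in general or will mostly be chance.

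**The arm effect has its own test, and omitting a randomised arm does not systematically confound baseline predictors.** Both are true, and at the planned 20-point difference arm is rarely dropped. The plan also does not state that arm must pass the screen; it is silent. But silence leaves an analyst free to drop it, and for a smaller true difference that would happen often.

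**Conclusion.** The concern holds in a limited form for a supplementary analysis. The outcome used for screening is undefined, and becomes a genuine mismatch only if seroconversion means negative to positive and some participants are IgG positive on Day 1. Selection at P < 0.2 followed by testing at 0.05 makes P values for retained variables too optimistic (about 25% rather than 5% for a null variable that passes). It inflates weak effects (about 1.35 times the true log odds ratio at 1.3 per SD, against 1.08 unscreened) and leaves strong ones nearly intact. Arm could be left out in about 44-45% of trials at a true 10-point difference and about 4-6% at 20 points; Day 1 IgG is equally unprotected.

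The sizes rest on assumed candidate numbers, effect sizes and Day 1 positivity. A reader might infer that the main result is in doubt. It is not: the chi-square comparison of arms and the sample size do not depend on this model. The change is worth making because it is cheap and the factor list will be published.

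**What to change.** Revise the statistical paragraph of section 14 as follows.

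1. Use Day 28 IgG positivity as the outcome in both the univariate and the multivariable step. Define seroconversion as negative on Day 1 and positive on Day 28, and analyse it separately in Day 1-negative patients.
2. Replace the P < 0.2 screen with a short list of clinical variables fixed in advance and sized to the expected 56-74 non-responders, about 5-7 parameters in total at an assumed 10 events each. Arm and Day 1 IgG use at least two of these, leaving about 3-5. Multi-category variables count for more than one: five organ types would take four parameters.
3. Include randomised arm and Day 1 IgG in the model whatever their P values. Enter Day 1 IgG as titre, or use penalised logistic regression if nearly all Day 1-positive patients remain positive and ordinary estimates become unstable.
4. Label the model and the univariate results exploratory, and report estimates with confidence intervals.

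The cost is wording only, since the serology is already being collected. The real price is that the list must be fixed before the data are seen, so an unanticipated factor could be reported only as a post hoc observation.

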1.1.2 Relationship to Study Intervention

All AEs and SAEs whether volunteered by the subject, discovered by study personnel during questioning, or detected through physical examination, laboratory test, or other means will be reported appropriately. Each reported AE or SAE will be described by its duration (i.e., start and end dates), regulatory seriousness criteria if applicable, suspected relationship to the study drug (see following guidance), and actions taken.

To ensure consistency of AE and SAE causality assessments, investigators should apply the following general guideline:

Yes [Definite, Probable, Possible]

IRB Study Number: 20210641
Version #4, Date: October 26, 2021

There is a plausible temporal relationship between the onset of the AE and administration of the study drug, and the AE cannot be readily explained by the subject's clinical state, intercurrent illness, or concomitant therapies; and/or the AE follows a known pattern of response to the study drug or with similar treatments; and/or the AE abates or resolves upon discontinuation of the study drug or dose reduction and, if applicable, reappears upon re- challenge.

No [Unrelated, Unlikely etc]

Evidence exists that the AE has an etiology other than the study drug (e.g., preexisting medical condition, underlying disease, intercurrent illness, or concomitant medication); and/or the AE has no plausible temporal relationship to {study drug} administration (e.g., cancer diagnosed 2 days after first dose of study drug).

Expected adverse events are those adverse events that are listed or characterized in the Package Insert (P.I) or current Investigator Brochure (I.B).

Unexpected adverse events are those not listed in the P.I or current I.B or not identified. This includes adverse events for which the specificity or severity is not consistent with the description in the P.I. or I.B. For example, under this definition, hepatic necrosis would be unexpected if the P.I. or I.B. only referred to elevated hepatic enzymes or hepatitis.

For patients receiving combination therapy, causality will be assessed individually for each protocol-mandated therapy.

All adverse events (AEs) must have their relationship to study intervention assessed by the clinician who examines and evaluates the participant based on temporal relationship and his/her clinical judgment. The degree of certainty about causality will be graded using the categories below. In a clinical trial, the study product must always be suspect.

Definitely Related – There is clear evidence to suggest a causal relationship, and other possible contributing factors can be ruled out. The clinical event, including an abnormal laboratory test result, occurs in a plausible time relationship to study intervention administration and cannot be explained by concurrent disease or other drugs or chemicals. The response to withdrawal of the study intervention should be clinically plausible. The event must be pharmacologically or phenomenologically definitive, with use of a satisfactory procedure if necessary.

Probably Related – There is evidence to suggest a causal relationship, and the influence of other factors is unlikely. The clinical event, including an abnormal laboratory test result, occurs within a reasonable time after administration of the study intervention, is unlikely to be attributed to concurrent disease or other drugs or chemicals, and follows a clinically reasonable response on withdrawal

IRB Study Number: 20210641
Version #4, Date: October 26, 2021

Potentially Related – There is some evidence to suggest a causal relationship (e.g., the event occurred within a reasonable time after administration of the trial medication). However, other factors may have contributed to the event (e.g., the participant’s clinical condition, other concomitant events). Although an AE may rate only as “possibly related” soon after discovery, it can be flagged as requiring more information and later be upgraded to “probably related” or “definitely related”, as appropriate.

Unlikely to be related – A clinical event, including an abnormal laboratory test result, whose temporal relationship to study intervention administration makes a causal relationship improbable (e.g., the event did not occur within a reasonable time after administration of the study intervention) and in which other drugs or chemicals or underlying disease provides plausible explanations (e.g., the participant’s clinical condition, other concomitant treatments).

Not Related – The AE is completely independent of study intervention administration, and/or evidence exists that the event is definitely related to another etiology. There must be an alternative, definitive etiology documented by the clinician.

1.1.3 Expectedness

The Sponsor-Investigator will be responsible for determining whether an adverse event (AE) is expected or unexpected. An AE will be considered unexpected if the nature, severity, or frequency of the event is not consistent with the risk information previously described for the study intervention.

1.1.4 Time Period and Frequency for Event Assessment and Follow-Up

The occurrence of an adverse event (AE) or serious adverse event (SAE) may come to the attention of study personnel during study visits and interviews of a study participant presenting for medical care, or upon review by a study monitor.

All AEs will be captured on the appropriate case report form (CRF) as well as in the Adverse Event reporting section in Velos, a HIPAA AND 21 CFR part 11 compliant database and will be reported to the University of Miami’s IRB per institutional requirements.

Any medical condition that is present at the time that the participant is screened will be considered as baseline and not reported as an AE. However, if the study participant’s condition deteriorates at any time during the study, it will be recorded as an AE.

Changes in the severity of an AE will be documented to allow an assessment of the duration of the event at each level of severity to be performed. AEs characterized as intermittent require documentation of onset and duration of each episode.

Study personnel will record all reportable events with start dates occurring any time after informed consent is obtained until 7 (for non-serious AEs) or 30 days (for SAEs) after the last day of study participation. At each study visit, the investigator will inquire about the

IRB Study Number: 20210641
Version #4, Date: October 26, 2021

occurrence of AE/SAEs since the last visit. If the investigator should become aware of the development of cancer or a congenital anomaly in a subsequently conceived offspring of a female subject, including pregnancy occurring in the partner of a male study subject who participated in the study, this should be reported as an SAE adequately to Genentech drug Safety during follow up period. Events will be followed for outcome information until resolution or stabilization.

